## **1.5 hypotheses**

### **1.5.1 NULL HYPOTHESIS (H0)**

Pilates Method exercise program has no clinical effect on peripheral muscle strength and endurance and does not reduce fatigue or dyspnea in patients with post-COVID syndrome.

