### **1.5.2 ALTERNATIVE HYPOTHESIS (H1)**

A quarterly Pilates Method exercise program has clinical effects on peripheral muscle strength and endurance, reducing fatigue and dyspnea in patients with post-COVID syndrome.

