## 2.4.2 secondary outcome

Improved quality of life (Questionnaire SF36) and reduced perception of dyspnea during physical activities and ADLs ( mMRC and Borg ).

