## 2.5 Data analysis

### 2.5.1 Sample size (calculation or justification)

The sample size calculation was done with the “ pwr ” package (CHAMPELY S, 2018) (R package , version 1.2-2, <https://CRAN.R-project.org/package=pwr> ). For the calculation, we considered the mean of 41.3, the standard deviation of 5.05 and a minimal clinically important difference of 4.7 kg between the means of maximum load in the maximal voluntary contraction test (OLIVEIRA IO, 2016) and power based on *Cohen 's model* of 0.8 with a standard deviation of 5.05. Assuming  $\alpha = 0.05$ ,  $\beta = 0.8$ , standard deviation = 5.05 and an effect size proposed by Cohen of 0.93.

This effect size " *d* " is calculated by:

$$d = [(Reference\ average + Minimum\ detected\ change) - reference\ average] / deviation - standard$$

$$d = [( 41.3 + 4.7) - 41.3] / 5.05 \Rightarrow d = 0.93.$$

*pwr* package . in R we have:

```
n = pwr.t.test ( n=NULL, d=0.93, sig.level =0.05, power=0.8, type=" two.sample ", alternative="
two.sided ")
```

$$n = 19.15925$$

$$d = 0.93$$

$$sig.level = 0.05$$

$$power = 0.8$$

$$alternative = two.sided$$

In this way, we use on=established and rounded up to the first integer immediately higher ( $n=20$ ) + 20% to cover any losses. Thus, the minimum number of patients needed in each group will be 24 patients.

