### **2.5.5 Statistical analysis plan**

Data analysis will be performed using the SPSS 23.0 program ( Statistical Package for Social Sciences ). Descriptive analysis will be performed for all variables (mean and standard deviation). General Linear Model ( GLMs ) with mixed design will be performed to compare treatment effect size between groups. The pairwise comparison comparisons ) will be performed to verify the mean difference between the Pilates Group and the Control Group in all variables in each period independently.

Intention-to-treat analysis was used using the *Last method. observation Carried Forward* (LOCF) for lost participant data. A significance level of 0.05 and a confidence interval of 95% will be adopted

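### The single H0 and H1 in section 1.5 are not complements, and section 2.5.5 has no rule linking its separate 0.05 tests to them, so one positive result could be read as support for all four effects

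*Combined protocol and SAP*

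**What the plan says.** - **Null (1.5.1).** One statement covers four effects: "Pilates Method exercise program has no clinical effect on peripheral muscle strength and endurance and does not reduce fatigue or dyspnea".
- **Alternative (1.5.2).** One statement asserts them together: the programme "has clinical effects on peripheral muscle strength and endurance, reducing fatigue and dyspnea in patients with post-COVID syndrome".
- **Analysis (2.5.5).** Pairwise group comparisons are made "in all variables in each period independently", and "A significance level of 0.05 and a confidence interval of 95% will be adopted". The section gives no test order, multiplicity adjustment, exploratory label or success criterion, and it does not mention H0 or H1.
- **Primary outcome (2.4.1).** Functional performance, formed from PCFS, hand dynamometry, quadriceps strength and quadriceps endurance. No combination rule is given.
- **Secondary outcomes (2.4.2).** SF-36 quality of life and "reduced perception of dyspnea during physical activities and ADLs".
- **Sample size (2.5.1).** Based on quadriceps maximum load alone: a 4.7 kg difference, SD 5.05, two-sided 0.05, power 0.8, giving 24 per group.

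**The concern.** A null and its alternative should cover the possibilities between them, so that rejecting one supports the other. Here a partial benefit fits neither. Evidence on any one component contradicts H0, but H1 needs all four, and the plan does not say what a mixed set of results would mean.

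The hypothesis also does not match the outcome lists. PCFS is a primary component but is absent from 1.5. Dyspnea is in 1.5 but is only a secondary outcome. Fatigue is in 1.5 but in neither outcome list.

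What is at stake is the reach of the conclusion. A significant strength result could be reported under a hypothesis that also says fatigue and dyspnea fell, while the symptom tests showed nothing.

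**Working it through.** **1. The plan's own figure.** d = 4.7/5.05 = 0.93. A two-sample, two-sided t test at 0.05 with power 0.8 gives n = 19.16, rounded up to 20; 20 × 1.2 = 24 per group. The plan's figure reproduces. At 24 per group with no losses, power for maximum load is 88%. (Section 2.3 gives 30 per group, which needs reconciling with 2.5.1 but does not change the error rates in step 3.)

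**2. The logic, case by case.**

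| Truth | H0 | H1 |
|---|---|---|
| No effect on any of the four | true | false |
| Some but not all four improve | false | false |
| All four improve | false | true |

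The middle row is the gap.

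**3. Error rate if any one positive test were taken to reject H0.** Assumptions: one two-sided 0.05 test for each of strength, endurance, fatigue and dyspnea; normal test statistics; a common correlation ρ between them. The documents give no value for ρ, so a range is shown.

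- Independent tests: 1 − (1 − 0.05)^4 = 1 − 0.8145 = 18.5%.
- Correlated tests: 1 − ∫ φ(u)·[Φ((1.96 − √ρ·u)/√(1−ρ)) − Φ((−1.96 − √ρ·u)/√(1−ρ))]^4 du.
- Counting only results in favour of Pilates, independent: 1 − (1 − 0.025)^4 = 9.6%, against a nominal 2.5%.

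| ρ | Either direction | In favour of Pilates |
|---|---|---|
| 0 | 18.5% | 9.6% |
| 0.3 | 17.4% | 8.7% |
| 0.5 | 15.6% | 7.8% |
| 0.8 | 11.4% | 5.7% |

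At ρ = 1 the either-direction rate falls to 5%. Simulated t tests with 24 per arm agree with the table to within about 0.3 percentage points.

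Four is the count of named effects. Counting the measures listed for them (grip in each hand, 1RM, endurance, two Pictogram items, mMRC) gives seven tests: 1 − 0.95^7 = 30.2% if independent, and about 15% at ρ = 0.8.

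**4. Only strength works, at the sized effect.** With independent tests, P(at least one p < 0.05) = 1 − (1 − 0.884) × 0.95^3 = 1 − 0.116 × 0.857 = 90%. Simulation gives 90% to 92% for ρ from 0 to 0.8, so this figure hardly depends on the assumed correlation. All four tests are significant in fewer than 1% of these trials. H0 is false here, so rejecting it is correct; H1 is also false.

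**5. Cost of a Holm adjustment across four tests.** The strictest step is 0.05/4 = 0.0125. Power for maximum load at 24 per arm falls from 88% to 73%.

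**The case against.** The strongest reply is that the documents contain no faulty decision rule, only silence. That stands. A reader might infer that the plan lets any single p < 0.05 reject H0 and so establish H1, but no section says this. The rates in steps 3 and 4 are conditional on that reading.

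A reader might also take a single figure such as 16% as the false-positive rate of the four-part claim. The documents do not support this. That value needs a common correlation of about 0.46, which they do not give. It applies only when no effect exists at all, and it counts results against Pilates.

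A third inference is that H1 drives the trial's conclusion. The Summary gives a differently worded alternative that includes exercise tolerance, balance and quality of life, and section 2.6 speaks of hypotheses in the plural without a decision rule. Nothing ranks section 1.5 above the outcome hierarchy in 2.4, which already makes dyspnea secondary. The text is also a rough translation, so its exact use of conjunctions should not carry much weight.

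Finally, the arithmetic uses normal outcomes and t tests, whereas mMRC is an ordinal 0 to 4 grade and the plan names a mixed-design GLM. The percentages are therefore approximate.

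None of this removes the gap between H0 and H1, the mismatch with 2.4, or the lack of any rule for several tests at 0.05.

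**Conclusion.** The concern holds as a missing rule and a mismatch. H0 and H1 leave partial benefit unassigned, 2.5.5 does not say how its tests bear on them, and the effects in 1.5 do not correspond to the outcomes in 2.4.

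If any one of four tests were taken to reject H0, the error rate with no effect would be about 11% to 19% for correlations from 0.8 down to 0, or about 6% to 10% counting only results in favour of Pilates (nominal 2.5%). In the strength-only case at the effect the trial is sized for, about 90% of trials would give a significant result under an H1 that is false. The correlations, the count of four tests and the normal model are assumptions. This should be corrected before analysis; it does not undermine the design or the sample size calculation.

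**What to change.** **Section 1.5.** Replace the single pair with one H0/H1 per outcome. Align the set with 2.4.1 and 2.4.2, and state where PCFS, handgrip, SF-36 and fatigue belong.

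**Section 2.5.5.** State a fixed sequence at two-sided 0.05:
1. quadriceps maximum load, the variable that 2.5.1 sizes the trial on;
2. the other 2.4.1 components (endurance, handgrip, PCFS), in a named order;
3. the 2.4.2 secondary outcomes, in a named order, with the SF-36 score specified.

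Confirmatory claims stop at the first p ≥ 0.05. Everything after that point, and fatigue, is labelled exploratory. Each conclusion covers only the outcome whose own null was rejected.

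Section 2.4.1 needs matching wording, because it now describes a combination without a rule. Borg cannot enter a between-group sequence as planned, since 2.3.8 limits it to the Pilates sessions.

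**Cost.** Wording in 1.5, 2.4 and 2.5.5; no new patients, data or procedures. The downside is that later outcomes, including dyspnea, can be claimed only if the earlier steps succeed. Holm across four outcomes is possible, but the power loss for maximum load (88% to 73% at its strictest step) makes the fixed sequence preferable.

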### **1.5.2 ALTERNATIVE HYPOTHESIS (H1)**

A quarterly Pilates Method exercise program has clinical effects on peripheral muscle strength and endurance, reducing fatigue and dyspnea in patients with post-COVID syndrome.

## **CHAPTER 2 - Participants and Methods**

### **2.1 Ethical aspects**

This clinical trial will be submitted to the Ethics and Research Committee of UNISUAM before the execution of the study, in accordance with resolution 466/2012. All voluntary participants, after all clarifications, will sign an informed consent form (ICF; Appendix 1) after being informed about the nature of the study and the protocol to be carried out.

### **2.2 Study design**

The study will be a clinical trial previously randomized by electronic randomization system ( [www.random.org](http://www.random.org) ) and the allocation of volunteers in the study arms will be done without the participation of the researchers. The study will be double-blind since neither the volunteers nor the professional who will perform the pilates protocol are aware of the objectives and clinical valences that will be measured by the study.

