## Summary

**Introduction:** COVID-19 is an emerging pandemic disease caused by severe acute respiratory syndrome (SARS-CoV-2). Although most patients infected with SARS-CoV-2 are asymptomatic or have mild symptoms, some patients develop severe symptoms that can long-term impair their quality of life and functional capacity. SARS-CoV-2 is closely related to severe acute respiratory syndrome (SARS) with direct and indirect effects on several systems, especially the musculoskeletal system, in addition to the respiratory system. Some of these symptoms persist for a long time, called Post-Covid-19 Syndrome, directly interfering with the functional capacity and quality of life of these patients. Pilates exercises focus on breathing, postural symmetry, trunk stabilization, flexibility, joint mobility and strengthening through the full range of motion of all joints and not isolated muscle groups. **Objectives:** The objective of this study will be to evaluate the clinical and functional effects of a Pilates exercise program for patients with Post-Covid-19 syndrome after a period of intensive care admission and invasive mechanical ventilation. **Methods:** The study will be a clinical, randomized and controlled trial. 48 patients of both sexes, over 18 years of age, who have developed the severe form of COVID-19 and required at least 7 days of invasive mechanical ventilation will be recruited. Patients who currently require supplemental oxygen at home and who present motor, cognitive or neurological alterations that prevent the practice of Pilates will be excluded. They will be previously randomized in a 1:1 ratio by electronic system and blindly allocated to the intervention group that will perform an exercise protocol based on the Pilates method, 2x/week, for 12 weeks in therapeutic sessions of identical protocols lasting 60 min. All patients will be evaluated before and after for peripheral muscle strength and endurance, post-Covid-19 functional status, dyspnea, fatigue and quality of life. Data analysis will be performed using the SPSS 23.0 program ( *Statistical Package for Social Sciences* ). Descriptive analysis will be performed for all variables (mean and standard deviation). *General Linear Model* ( GLMs ) with mixed design will be performed to compare treatment effect size between groups. The *pairwise comparison comparisons* ) will be performed to verify the mean difference between the Pilates Group and the Control Group in all variables in each period independently. Intention-to-treat analysis was used using the *Last method. observation Carried Forward* (LOCF) for lost participant data. A significance level of 0.05 and a confidence interval of 95% will be adopted. **Results:** The expected results are based on the alternative hypothesis that Pilates exercises are clinically effective, improving functional performance, exercise tolerance, balance, reducing symptoms and improving the quality of life of patients with symptoms of Post-Covid-19 Syndrome.

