## **2.3 Sample**

The sample will consist of 60 participants, divided into two groups: an intervention group (n=30) that will do a 12-week program, 2x/week of Pilates method exercises , and a control group (n=30) that will not do any intervention for rehabilitation in the period.

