### **2.3.3 Exclusion criteria**

1. Need for supplemental home oxygen;
2. Motor or neurological or cognitive alteration that contraindicates the practice of Pilates .
3. Persistence of clinical signs of deep vein thrombosis
4. Upper limb dynamometry < 14 kg for men and < 7 kg for women would indicate very marked peripheral muscle weakness and would therefore contraindicate Pliates at the moment.

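### The per-period strength comparisons adjust for neither sex nor baseline, and no stratified allocation is described; for grip this costs precision but not validity

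*Combined protocol and SAP*

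**What the plan says.** **Allocation.** Section 2.2: "The study will be a clinical trial previously randomized by electronic randomization system". The Summary says patients are "previously randomized in a 1:1 ratio by electronic system". Section 2.2 names the random.org site and keeps the researchers out of the allocation. Strata, blocks and minimisation are not mentioned.

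**Sex and strength.** Both sexes are eligible. Section 2.3.6.1 gives prediction equations with a sex term of 13.628 kgf for the dominant hand and 9.274 kgf for the non-dominant hand. Section 2.3.3 sets sex-specific limits: "Upper limb dynamometry < 14 kg for men and < 7 kg for women". Section 2.4.1 makes grip one of four components of the primary outcome, with the PCFS, quadriceps strength and quadriceps endurance.

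**Analysis.** Section 2.5.5 plans a mixed-design general linear model and then pairwise comparisons of "the mean difference between the Pilates Group and the Control Group in all variables in each period independently". It names no covariates and does not say which model term is primary. Section 2.5.4 does not list sex as a confounder. Section 2.5.2 calls the outcome measures control variables but does not say that their baseline values enter a model.

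**Size.** The Summary has "48 patients of both sexes, over 18 years of age". Section 2.5.1 concludes that "the minimum number of patients needed in each group will be 24 patients". Section 2.3 differs: "The sample will consist of 60 participants, divided into two groups".

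**The concern.** The protocol itself treats sex as a strong determinant of grip, but neither the described allocation nor the stated analysis uses it. With 24 per arm the numbers of men will often differ by several. In a 12-week comparison that ignores both sex and baseline, each extra man in one arm moves the difference in mean dominant grip by 13.628/24 = 0.57 kg. At stake is how precisely grip can be compared between arms, and how readily readers will accept a result from arms that visibly differ in sex.

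**Working it through.** **1. The plan's own figure.** Section 2.5.1 uses "sig.level =0.05, power=0.8", two-sided, with d = 4.7/5.05 = 0.93. A noncentral-t calculation gives n = 19.159 per arm, as stated. Rounded up, 20 × 1.2 = 24. The 4.7 kg and 5.05 kg belong to the quadriceps maximum-load test, not to grip.

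**2. Inputs for grip.** 24 per arm (Summary and section 2.5.1); sex gaps of 13.628 and 9.274 kgf (section 2.3.6.1, at equal age and weight, assumed to hold in these patients). The documents give no grip SD, so 5.05 kg is assumed as the within-sex SD. It cannot be the overall SD at 50% men, because the sex gap alone would then give 0.5 × 13.628 = 6.81 kg. The share of men is not stated; 50% to 90% is examined.

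**3. Within-sex standard error.** 5.05 × √(2/24) = 1.46 kg.

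**4. Chance shift from sex imbalance.** In a random 24:24 split with proportion p of men among 48, the number of men in one arm has SD √(24 × p(1−p) × 24/47). Multiplying by 2/24 gives the SD of the difference in proportions of men; multiplying that by the sex gap gives the shift. At p = 0.5: √(24 × 0.25 × 24/47) = 1.750; × 2/24 = 0.1459; × 13.628 = 1.99 kg.

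| Men of 48 | Dominant: SD of shift, kg (ratio to 1.46) | Non-dominant: SD of shift, kg (ratio) |
|---|---|---|
| 24 (50%) | 1.99 (1.36) | 1.35 (0.93) |
| 34 (about 70%) | 1.81 (1.24) | 1.23 (0.84) |
| 38 (about 80%) | 1.61 (1.11) | 1.10 (0.75) |
| 43 (about 90%) | 1.21 (0.83) | 0.83 (0.57) |

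At 50% men the arms differ by 6 or more men in about 15% of allocations, a dominant-grip shift of at least 6 × 13.628/24 = 3.41 kg.

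**5. Variance inflation of the unadjusted comparison,** 1 + ratio². For the dominant hand at 50% men this is 1 + 1.36² ≈ 2.9; for the non-dominant hand, 1 + 0.93² ≈ 1.9. If the within-sex SD is 10 kg, the standard error is 10 × √(2/24) = 2.89 kg and the dominant-hand inflation at 50% men falls to 1 + (1.99/2.89)² ≈ 1.5.

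**6. What adjustment recovers.** Simulated standard error of the dominant-grip treatment difference, 24 per arm, within-sex SD 5.05, assumed within-sex pre-post correlation 0.7:

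| Analysis | 50% men | 80% men |
|---|---|---|
| 12-week value, unadjusted | 2.46 | 2.18 |
| 12-week value, sex in model | 1.49 | 1.48 |
| Change from baseline | 1.13 | 1.13 |
| 12-week value, baseline in model | 1.11 | 1.10 |

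The first entry agrees with √(1.99² + 1.46²) = 2.47. Baseline does better than sex alone once the correlation is about 0.5 or higher. Simulated type I error was about 5% for both the unadjusted 12-week test and the change test.

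**7. If 60 patients are enrolled.** At 30 per arm the dominant-hand ratios are 1.36, 1.09 and 0.82 at 50%, 80% and 90% men, so the conflict over N does not alter the picture.

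**The case against.** The strongest reply is that section 2.5.5 opens with a mixed-design model on before-and-after data. A constant sex offset cancels in its group-by-time term, where stratifying by sex adds almost nothing. This stands. But the plan does not name that term as the primary test, and it explicitly adds the per-period comparisons, which are exposed.

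Second, the prediction equations could be used to express grip relative to sex. They could, but section 2.3.6.1 takes the highest value for each hand for analysis, and no percent-predicted endpoint is defined.

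Several stronger readings are tempting and are not supported:

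- *That imbalance can readily create or hide an effect of the size sought.* The 4.7 kg is a quadriceps figure. A dominant-grip shift above it occurs in 0.9% of allocations with 24 men of 48, 1.7% with 29 and under 0.1% with 38.
- *That false positives increase.* Chance imbalance is already part of the sampling error of an unadjusted test.
- *That the shift always exceeds the within-sex error.* It does not for the non-dominant hand, nor for the dominant hand at about 90% men.
- *That all the strength measures are affected alike.* No sex gap is given for quadriceps strength or endurance. Section 2.3.6.2 normalises the one-repetition maximum by body weight, and section 2.3.6.3 sets the endurance load at 40% of the patient's own maximum.
- *That the list is certainly unstratified.* The documents are silent; if strata exist, stating them settles that part.

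**Conclusion.** The point holds as a matter of efficiency and of incomplete specification. Followed as written, the unadjusted 12-week comparison of dominant grip has a standard error of about 2.46 kg at 50% men. Adding sex brings it to 1.49 kg and adding baseline to 1.11 kg. The loss is smaller for the non-dominant hand, with a higher share of men, or with a larger within-sex SD, but it is not zero. The size rests on three assumptions: a within-sex SD of 5.05 kg borrowed from the quadriceps test, the equations' sex gaps applying to these patients, and, for the baseline gain, a pre-post correlation of 0.7. How far grip affects the primary result cannot be calculated, because section 2.4.1 gives no rule for combining its four components. The change is worth making because it is cheap, not because the trial would otherwise be invalid.

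**What to change.** **Section 2.5.5.** Make the between-arm comparison of each strength outcome at 12 weeks a model with the baseline value and sex as covariates. Alternatively, name the group-by-time term as the primary test. Baseline is the more valuable covariate under the assumptions above; sex should accompany it because it is a stratification factor.

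**Section 2.2.** State the randomisation method. Before the first enrolment, generate the list in two strata (men, women) with permuted blocks of varying size, concealed and held by the person outside the research team who allocates. If the blocks keep the arms within 2 men of each other, the dominant-grip shift is at most 2 × 13.628/24 = 1.14 kg. Blocking also keeps the arms close to equal size. State one total sample size so that the list has a defined length.

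**Cost.** A new allocation list and two covariates; no extra patients, visits or measurements. Stratification has to be in place before enrolment. The model can be specified later, but should be fixed before any outcome data are examined by arm.

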### **2.3.6 Peripheral Muscle Assessment**

#### **2.3.6.1 Palm grip dynamometry**

Traditionally, handgrip strength (HGS) tests have been used in rehabilitation to assess the physical condition of the upper limbs, by measuring the strength of the hand and forearm muscles of patients with various disorders in the upper extremity resulting from arthritis, rheumatoid disease , carpal tunnel syndrome, lateral epicondylitis , stroke, traumatic injuries, myopathy , ICU-acquired muscle weakness, critical patient polyneuropathy and neuromuscular diseases (INNES E, 1999; KURILLO GA *et al* ., 2004; MOREIRA D *et al.*, 2004; MOREIRA D *et al.* *al* ., 2003) HGS measurement by

dynamometry presents a good correlation with the functional level of the upper limbs and general health status, being widely used in the selection of therapeutic procedures and monitoring of functional rehabilitation (INNES E, 1999). Manual dynamometry has wide applicability, as it is a low-cost, simple, fast and non-invasive method (GÜNTHER CM *et al.*, 2008) that provides, through HGS values, an indicator of the general health of the evaluated individuals.

The HGS assessment will be performed by a single previously trained investigator, in the morning between 8 am and 12 noon, according to the recommendations of the Brazilian Society of Hand Therapists (SBTM, 2008). The individuals will be positioned seated with the arm adducted parallel to the trunk, shoulder in neutral rotation, elbow flexed at 90°, forearm in fundamental position. Wrist hyperextension of up to 30° and ulnar deviation of up to 15° will be allowed during the tests. Three measurements will be taken from both hands, with a minimum interval of 30 seconds between them. The tests will be performed alternately between the dominant and non-dominant side, to minimize the influence of muscle fatigue. For data analysis, the highest value obtained for each hand will be considered. The dominant hand is defined as the preferred hand for carrying out daily activities. Volunteers will be asked which hand they prefer to carry out activities such as writing, eating and carrying objects. During the execution of the handgrip, the arm will remain immobile, with only permission for the movement of the wrist and finger joints.

Will be used as prediction formulas (NOVAES RD *et al.*, 2009):

- $HGS-D,_{kgf} = 39.996 - (0.382 \times age,_{years}) + (0.174 \times weight,_{kg}) + (13.628 \times sex \text{ (men=1; women=0)})$

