### **2.3.11 Pilates Method Exercise Protocol (MP)**

Pilates exercise protocol : was developed based on protocols contained in previously published clinical trials whose objective was muscle strengthening or improvement of muscle fatigue. Thus, the protocol developed will perform exercises from the classical repertoire of the Pilates Method, with the use of equipment exclusive

to the Method - such as *Cadillac* , *Ladder Barrel* , *Chair and Reformer* . The sessions will take place twice a week, in groups of up to 3 participants, always in the morning and will last 60 min, with 10 min of warm-up, 40 min of exercises with load and 10 min of relaxation exercises and calm down. All sessions will be performed by a physical therapist specialized in the method, in a specific outpatient clinic. The professional who will conduct the Pilates sessions will execute the proposed protocol and is unaware of the outcomes studied by the project. In figure 3, we present the equipment that will be used in the study.

**Figure 3:** Equipment that will be used. (a) *Combo Chair* , (b) *Cadillac* , (c) *Universal Reformer* , (d) *Ladder barrel*

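### The double-blind label in section 2.2 rests on not knowing the objectives, not on not knowing the arm, and no available section masks whoever tests the four primary components

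*Combined protocol and SAP*

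**What the plan says.** Section 2.2 gives one reason for the label: "The study will be double-blind since neither the volunteers nor the professional who will perform the pilates protocol are aware of the objectives" and of what will be measured. Section 2.3.11 repeats the idea for the therapist, who "is unaware of the outcomes studied by the project".

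Two other statements use the language of concealment. Section 2.2 says that "the allocation of volunteers in the study arms will be done without the participation of the researchers", and the Summary says that patients are "blindly allocated to the intervention group".

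The control group is one "that will not do any intervention for rehabilitation in the period" (section 2.3). For the Pilates arm, "The sessions will take place twice a week, in groups of up to 3 participants, always in the morning" (section 2.3.11), on apparatus and led by a physical therapist.

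Section 2.4.1 defines the primary outcome as a combination of PCFS, handgrip dynamometry, quadriceps strength and quadriceps endurance. On testers, section 2.3.6.1 says: "The HGS assessment will be performed by a single previously trained investigator, in the morning between 8 am and 12 noon". Section 2.3.7 assigns PCFS to a trained evaluator. Sections 2.3.6.2 (1RM) and 2.3.6.3 (endurance) name no tester. Section 2.5.5 does not mention masking.

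**The concern.** Blinding means not knowing which arm a participant is in. The plan offers a different property, not knowing the objectives and measures, and gives it the name of the first. A reader of the registry entry or the paper would credit the trial with protection that its design cannot give to participants or therapist.

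The label also hides a gap that could be closed. When treatment cannot be masked, the usual safeguard is a tester who does not know the arm. It matters here because the literature review, in its text on maximum voluntary contraction, calls these tests volitional and accepts that motivation can lead to submaximal effort. A tester who knows the arm could encourage more strongly, offer a further attempt, or judge failure differently, without intending to.

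**Working it through.** This is mainly a reading of the sections against each other.

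**Step 1. Can participants and therapist be masked?** The contrast is supervised apparatus sessions of 60 minutes, twice a week for 12 weeks, against no rehabilitation. No sham or attention control is described. A participant knows whether he or she attends, and everyone the therapist treats in the programme is in the Pilates arm. No section states that they know the arm, but it follows directly from the design. Even the stated basis is weak: section 2.1 says volunteers are informed of the nature of the study and of the protocol.

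**Step 2. Do the other statements help?** Allocation without the researchers and blind allocation describe how the arm is assigned. They do not say who may know it at the assessment after 12 weeks.

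**Step 3. Are the testers masked?**

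| Primary component | Section | Tester named | Masking stated | Depends on participant through |
|---|---|---|---|---|
| Handgrip | 2.3.6.1 | single trained investigator | no | effort |
| Quadriceps 1RM | 2.3.6.2 | none | no | effort |
| Quadriceps endurance | 2.3.6.3 | none | no | effort |
| PCFS | 2.3.7, Annex 1 | trained evaluator | no | answers |

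Tester masking is stated for 0 of 4 components. A tester role is named for 2 of 4. Effort tests plus the scale based on answers: 3 + 1 = 4 of 4 depend in part on an unmasked participant, so masking the tester protects only the tester's share.

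**Step 4. Does the sample size move?** From section 2.5.1, d = 4.7 / 5.05 = 0.93. A two-sided two-sample t-test at 0.05 with power 0.80 gives n = 19.16, rounded up to 20, and 20 × 1.2 = 24 per group. The plan's figure reproduces, and masking the testers does not change it.

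**Step 5. How large could the bias be?** The documents give no basis for an estimate. As an illustration only, assume no true effect and a shift of b kg in the 1RM difference caused by knowledge of the arm. The chance of a significant result is the power of the same t-test at d = b / 5.05, with noncentrality d × √(n/2). For n = 24 and b = 1, d = 0.198 and noncentrality = 0.198 × 3.464 = 0.69.

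| Assumed shift b | 24 per group | 30 per group (section 2.3) |
|---|---|---|
| 0.5 kg | about 6% | about 7% |
| 1.0 kg | about 10% | about 12% |
| 2.0 kg | about 27% | about 33% |

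These rates apply to 1RM alone, at the planning SD, and depend entirely on the assumed shift.

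**The case against.** The plan says in the same sentence what it means by double-blind, so an attentive reader can see the basis. Allocation without the researchers is a real partial safeguard. The tests are partly standardised: fixed posture and three trials per hand for grip, and a load of 40% of 1RM with a set cadence for endurance. The literature review also reports little variability in such tests. Testers may be masked in practice, and a few pages are not in the text available here.

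Of this, the allocation safeguard and the standardisation stand, but neither keeps the arm from a tester. The low variability is credited partly to verbal encouragement, which is something a tester can apply unequally, and low variability is not absence of a difference between arms. Explaining a label does not make it correct. Masking in practice would need to be written down.

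Three stronger readings are tempting and not supported:

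- A reader might infer that testers will see who trains, because grip testing and Pilates both take place in the morning. The grip hours apply to grip only, assessments are before and after the programme, and the documents do not say where tests are done relative to the clinic. That some group is training at a given hour does not reveal the arm of the person being tested.
- A reader might treat PCFS as a pure self-report that assessor masking cannot help. Section 2.3.7 mentions self-assessment as a general option, but in this trial a trained evaluator conducts the scale. It is evaluator-administered and based on the patient's answers (Annex 1), so masking the evaluator gives some protection.
- A reader might infer from section 2.3.11 that an independent tester is already available. It implies only that the therapist, being unaware of the outcomes, is not the tester. The budget table lists the Pilates physiotherapist as the only execution-team entry.

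**Conclusion.** The label is wrong as written, and it should be corrected. Participants and therapist know the arm, and no available section masks a tester for any of the four primary components. The first part is an inference from a control group with no intervention and no sham. The second assumes that the pages not available here do not cover assessor masking, which seems likely but cannot be checked.

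A reader might go further and conclude that the testers do know the arm or that the results will be biased. The documents support neither: they are silent on what testers know, and the size of any bias cannot be estimated from them. No figure in the plan changes.

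**What to change.** In section 2.2, replace the double-blind sentence with *open-label for participants and therapist*. State who performs each primary assessment, filling the gaps in sections 2.3.6.2 and 2.3.6.3. Require that these testers:

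- do not deliver Pilates sessions;
- have no access to the allocation list;
- use the same scripted encouragement in both arms;
- ask participants not to disclose their arm.

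With those rules in place, add *outcome assessors masked to allocation*. If existing staff cannot meet them, describe the trial as open-label and report this as a limitation. In either case, report that participant effort in the strength and endurance tests, and the answers behind PCFS, SF-36, mMRC and the Fatigue Pictogram, are unmasked.

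The cost is mostly wording and control of the allocation list. Whether current staff can supply a masked tester is not known from the documents, hence the fallback. The double-blind label is lost, and some participants may still reveal their arm.
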